Subjects in both cohorts will reduce the dose by one capsule per week, as necessary, and no more frequently than at biweekly intervals, in the event that any one of the following four criteria are met: plasma iPTH is confirmed to be <35 pg/mL (for subjects with stage 3 CKD) or <70 pg/mL (for subjects with stage 4 CKD), serum calcium (corrected) is confirmed to be >10.3 mg/dL, serum total 25-hydroxyvitamin D is confirmed to be >100 ng/mL, or serum phosphorus is confirmed to be >5.5 mg/dL (ages 12 to <18 years) or >6.0 mg/dL (ages 8 to <12 years), provided that the investigator has deemed the elevated serum phosphorus to be related to study drug administration and has taken appropriate and persistent actions to control serum phosphorus by initiating or adjusting any phosphate binder therapy.

Dose reductions will be accomplished by consistently omitting doses on a specific day of the week, as follows:

- First dose reduction: Dosing will be omitted on all Mondays (M).
- Second dose reduction: Dosing will be omitted on all M and Wednesdays (W)
- Third dose reduction: Dosing will be omitted on all M, W and Fridays (F)
- Fourth dose reduction: Dosing will be omitted on all M, W, F and Sundays (S)

Any subject who requires a further dose reduction will terminate dosing with study drugs and immediately commence the 6-week FU period.

Subjects on dose reduction will be allowed an unscheduled safety visit if deemed appropriate by the investigator to have FU blood sampling within 48 hours of any dose reduction.

A summary of the initial and reduced weekly dose levels, in mcg units, after each of the four possible dose reductions appears in the table below:

Daily (mcg)	Weekly (mcg)	Weekly Dose (mcg)			
		1 st Reduction	2 nd Reduction	3 rd Reduction	4 th Reduction
60	420	360	300	240	180
30	210	180	150	120	90
0	0	0	0	0	0

Subjects will suspend dosing if plasma iPTH is persistently <30 pg/mL (three consecutive visits) or serum calcium (corrected) is confirmed to be >11.0 mg/dL, and resume when iPTH is ≥ 35 pg/mL and serum calcium is <9.8 mg/dL at the next lower dose level.

Primary Efficacy Endpoint:

The primary estimand is the reduction of mean plasma iPTH by at least 30% from pre-treatment baseline. The primary efficacy endpoint is the proportion of subjects in the intent-to-treat (ITT) population (age 8 to <18 years) attaining a mean decrease in plasma iPTH of at least 30% from pre-treatment baseline compared to placebo during the EAP.

Primary Safety Endpoints:

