1.13 Clinical Efficacy and Safety

In CTAP101-CL-2008, a double-blind, placebo-controlled, randomized repeat-dose study, daily administration of CTAP101 Capsules increased serum total 25-hydroxyvitamin D levels to ≥ 30 ng/mL in nearly all subjects and decreased mean plasma intact PTH (iPTH) from baseline and compared to placebo during six weeks of treatment. The mean % decrease in iPTH from baseline was related to the administered dose: 20.2 ± 20.8 (standard deviation [SD]), 32.0 ± 22.3 , 37.9 ± 15.9 for the 30, 60 and 90 μg groups, respectively.

The efficacy was confirmed in the phase 3 program with nearly all CTAP101 Capsules subjects (97%), who completed the study without a deviation, achieving a normal serum total 25-hydroxyvitamin D level and with 60% of subjects achieving a mean reduction in iPTH from baseline of at least 30%. Fewer than 9% of placebo subjects achieved a 30% reduction in iPTH or achieved a normal 25-hydroxyvitamin D level.

CTAP101 Capsules did not cause significant adverse effects on serum calcium or phosphorus. Treatment-emergent adverse events (TEAEs), including those related to the investigational study drug, were comparable across treatment groups, except for hyperphosphatemia, which was observed in four subjects, none of which was considered by the investigator to be related to the study drug.

For all clinical studies, the AE profiles did not identify any events specific to CTAP101 Capsules. After both single and repeat-dose administration, CTAP101 Capsules was generally well-tolerated. The overall TEAE profile in the phase 3 program was comparable between CTAP101 Capsules and placebo groups. Subjects receiving CTAP101 Capsules had a greater mean (standard error [SE]) increase in serum calcium ($P < 0.001$) than placebo patients (ie, $0.2 [0.02]$ versus $0.1 [0.03]$ mg/dL); for serum phosphorus, subjects receiving CTAP101 Capsules had a greater mean (SE) increase ($P < 0.05$) than placebo patients ([ie, $0.2 [(0.03)]$ versus $0.1 [(0.04)]$ mg/dL]).

CTAP101 Capsules have not been previously studied in pediatric patients.

This protocol may be amended in due course to include subjects having ages less than 8 years.

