4.2 Inclusion Criteria

Each subject must meet the following criteria to be enrolled in this study:

1. Cohort 1: Be 12 to <18 years of age and have a body weight of ≥ 40 kg; Cohort 2: be 8 to <12 years of age and have a body weight of ≥ 20 kg.
2. Be diagnosed with stage 3 to 4 CKD at least six months prior to the screening visit, and have an eGFR of ≥ 15 to <60 mL/min/1.73m² at screening.
3. Be without any disease state or physical condition that might impair evaluation of safety or which, in the investigator's opinion, would interfere with study participation, including:
 - a. Serum albumin ≤ 3.0 g/dL;
 - b. Serum transaminase (ALT or SGPT, AST or SGOT) > 2.5 times the upper limit of normal at screening; and,
 - c. Urinary albumin excretion of >3000 mcg/mg creatinine.
4. Exhibit during the initial or, if necessary, a screening visit after washout:
 - a. Plasma iPTH >100 pg/mL (stage 3 CKD) or >160 pg/mL (stage 4 CKD)
 - b. Serum calcium <9.8 mg/dL (corrected for albumin);
 - c. Serum total 25-hydroxyvitamin D <30 ng/mL; and,
 - d. Serum phosphorus >2.5 to ≤ 5.5 mg/dL (12 to <18 years) or ≤ 6.0 mg/dL (ages 8 to <12 years);
5. If taking calcitriol or other 1 α -hydroxylated vitamin D analogs, or cinacalcet, be willing to forgo treatment with these agents for the duration of the study and complete an 8-week washout period prior to commencing treatment in the study.
6. If taking $>1,000$ mg/day of elemental calcium, discontinue or reduce calcium use and/or use non-calcium based therapies for the duration of the study.
7. If receiving $\leq 1,700$ IU/day nutritional vitamin D (ergocalciferol or cholecalciferol) therapy, must agree to remain on a stable dose during the study.
8. If taking $>1,700$ IU/day of nutritional vitamin D, must discontinue or decrease the dose to $\leq 1,700$ IU/day, maintain that dose for the duration of the study, and complete an 8-week washout period prior to commencing treatment in the study provided that serum total 25-hydroxyvitamin D is ≥ 30 ng/mL. The washout period is not necessary if serum total 25-hydroxyvitamin D is <30 ng/mL.
9. If taking any bone modifying treatment that could interfere with study endpoints, must discontinue use of such agent(s) for the duration of the study.

10. Willing and able to comply with study instructions and commit to all clinic visits for the duration of the study.

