5.3 Selection and Timing of Dose for Each Subject

Subjects in Cohort 1 will receive two capsules (CTAP101 Capsules and/or matching placebo capsules) every day at bedtime to achieve the targeted initial daily dose of 30 mcg of calcifediol (one CTAP101 Capsule plus one placebo capsule) or 0 mcg of calcifediol (two placebo capsules). Any food intake within 60 minutes of medication administration will also be recorded. At the end of 12 weeks of treatment, subjects assigned to active treatment will undergo upward dose titration to 60 mcg per day (two CTAP101 Capsules) provided that (a) plasma iPTH has not decreased by at least 30% from pretreatment baseline, (b) corrected serum calcium is <9.8 mg/dL, (c) serum phosphorus is \leq 5.5 mg/dL, and (d) serum total 25-hydroxyvitamin D is \leq 65 ng/mL. Subjects in Cohort 2 will receive a starting daily bedtime dose which will be determined on the basis of the interim analysis of data obtained in Cohort 1, and will undergo upward dose titration at the end of 12 weeks of treatment to a new daily dose that is two times higher than the starting dose, provided that (a) plasma iPTH has not decreased by at least 30% from pretreatment baseline, (b) corrected serum calcium is <9.8 mg/dL, (c) serum phosphorus is \leq 6.0 mg/dL and (d) serum total 25-hydroxyvitamin D is \leq 65 ng/mL.

In order to maintain blinding, subjects will receive periodic supplies of study drug in bottles of identical appearance, some labeled “Bottle 1” and some labeled “Bottle 2,” along with the same dosing instructions regardless of randomization group directing the subject to take one capsule from one bottle labeled “Bottle 1” and one bottle labeled “Bottle 2” every day at bedtime.

An unblinded medical monitor who will be part of the independent, unblinded DSMB will oversee study drug assignments and dose adjustments (see below) by IRS.

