5.4 Dose Reduction Criteria

Subjects will reduce the dose through the IRS by one capsule per week, as necessary, and no more frequently than at biweekly intervals, in the event that any one of the following four criteria are met:

1. Two consecutive visits with plasma iPTH <35 pg/mL (for subjects with stage 3 CKD) or <70 pg/mL (for subjects with stage 4 CKD),
2. Two consecutive visits with serum calcium (corrected) >10.3 mg/dL,
3. Two consecutive visits with serum total 25-hydroxyvitamin D >100 ng/mL, or
4. Two consecutive visits with serum phosphorus >5.5 mg/dL (ages 12 to <18 years), or >6.0 mg/dL (ages 8 to <12 years) provided that the investigator has deemed the elevated serum phosphorus to be related to study drug administration and has taken appropriate and persistent actions to control serum phosphorus by initiating or adjusting any phosphate binder therapy.

Dose reductions will be accomplished by consistently omitting doses on a specific day of the week, as follows:

- First dose reduction: Dosing will be omitted on all M.
- Second dose reduction: Dosing will be omitted on all M and W
- Third dose reduction: Dosing will be omitted on all M, W and F

- Fourth dose reduction: Dosing will be omitted on all M, W, F and S

Any subject who requires a further dose reduction will terminate dosing with study drugs and commence the 6-week FU period.

Subjects on dose reduction will be allowed a safety visit if deemed appropriate by the investigator to have FU blood sampling within 48 hours of dose reduction.

A summary of the initial and reduced weekly dose levels, in mcg units, after each of the four possible dose reductions appears in the table below:

Daily (mcg)	Weekly					Dose (mcg)
	Weekly (mcg)	1 st Reduction	2 nd Reduction	3 rd Reduction	4 th Reduction	
60	420	360	300	240	180	
30	210	180	150	120	90	
0	0	0	0	0	0	

Subjects will suspend dosing if plasma iPTH is persistently <30 pg/mL (three consecutive visits) or serum calcium (corrected) is confirmed to be >11.0 mg/dL, and resume when iPTH is \geq 35 pg/mL (for subjects with stage 3 CKD) or \geq 70 pg/mL (for subjects with stage 4 CKD) and serum calcium is \leq 9.8 mg/dL at the next lower dose level.

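### The Synopsis and Section 5.4 give different rules for resuming suspended study drug, so a stage 4 child with iPTH of 35 to 69 pg/mL is restarted under one text and held under the other

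*Combined protocol and SAP*

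**What the plan says.** The suspension trigger is the same in the Synopsis (Dosing Plan) and in Section 5.4: iPTH below 30 pg/mL at three consecutive visits, whatever the CKD stage, or confirmed corrected calcium above 11.0 mg/dL. Dosing then resumes one dose level down. The condition for resuming differs:

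- **Synopsis:** iPTH of at least 35 pg/mL for all subjects, provided "serum calcium is <9.8 mg/dL at the next lower dose level".
- **Section 5.4:** iPTH of at least 35 pg/mL in stage 3, but at least "70 pg/mL (for subjects with stage 4 CKD) and serum calcium is" no more than 9.8 mg/dL.

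Both texts share the dose-reduction triggers. These include confirmed iPTH below 35 pg/mL in stage 3; the Synopsis continues with "<70 pg/mL (for subjects with stage 4 CKD), serum calcium (corrected) is confirmed to be >10.3 mg/dL". Section 3.2 mentions reduction or suspension for over-suppressed iPTH but gives no rule for resuming. On oversight, Section 5.3 states: "An unblinded medical monitor who will be part of the independent, unblinded DSMB will oversee study drug assignments and dose adjustments".

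**The concern.** Both sentences are current protocol text, and no order of precedence is given. The rule decides when a child goes back on drug after the most serious dosing action short of permanent discontinuation. Section 1.13 says the product has not been studied in pediatric patients before.

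Under the Synopsis, a stage 4 child is restarted while iPTH may still be in the range that both texts treat, once confirmed, as reason to cut the dose. Under Section 5.4 the child stays off drug until iPTH reaches 70 pg/mL. If the IRS is programmed from one text and the DSMB verifies against the other, a restart could be judged correct by one and wrong by the other.

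**Working it through.** The plan states no figure to reproduce. The check sets the two rules side by side and then gauges how often the difference could matter.

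**1. Apply both rules to a suspended subject with calcium below 9.8 mg/dL.**

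| CKD stage | iPTH (pg/mL) | Synopsis | Section 5.4 |
|---|---|---|---|
| 3 | below 35 | hold | hold |
| 3 | 35 or more | resume | resume |
| 4 | below 35 | hold | hold |
| 4 | 35 to below 70 | **resume** | **hold** |
| 4 | 70 or more | resume | resume |

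The conflict is confined to stage 4 with iPTH from 35 to below 70 pg/mL. The calcium mismatch matters only at exactly 9.8 mg/dL, where the Synopsis holds and Section 5.4 permits resumption once the iPTH condition is met.

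**2. Which rule fits the rest of the plan?** The Section 5.4 thresholds (35 and 70) are the complements of the shared reduction triggers (below 35 and below 70). The single Synopsis threshold matches only the stage 3 trigger. For calcium, the Synopsis inequality (below 9.8 mg/dL) matches the entry criterion in Section 4.2 and the titration criterion in Section 5.3.

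**3. Would a suspended child reach the conflict range?** A stage 4 child suspended on iPTH has to rise from below 30 to 70 pg/mL, passing through 35 to 69. Sections 3.2 and 5.5 give a half-life of about 30 days in adults, and late treatment visits (Days 155, 169, 183) are 14 days apart. A visit could therefore fall in the range, although the documents do not give the speed of recovery. A child suspended for calcium could also have iPTH in this range.

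**4. How many might be suspended on iPTH?** The documents give no suspension rate, so this is an illustration only.

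- Active stage 4 subjects: 72 × 0.5 = 36 if the stages split evenly (assumption). At 30% the count is 72 × 0.3 ≈ 22, and at 70% it is 72 × 0.7 ≈ 50.
- Fall needed from the lowest eligible stage 4 baseline (above 160 pg/mL, Section 4.2): 1 − 30/160 = 81.25%.
- Six-week adult falls (Section 1.13): 20.2 ± 20.8% at 30 mcg and 32.0 ± 22.3% at 60 mcg. Assume normality and transfer to children.
- 30 mcg: z = (81.25 − 20.2)/20.8 = 2.935, upper tail 0.00167.
- 60 mcg: z = (81.25 − 32.0)/22.3 = 2.209, upper tail 0.0136.

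| Active stage 4 subjects | Expected, 30 mcg tail | Expected, 60 mcg tail |
|---|---|---|
| 22 | 0.04 | 0.30 |
| 36 | 0.06 | 0.49 |
| 50 | 0.08 | 0.68 |

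**5. Dose at restart.** A stage 4 child with three consecutive values below 30 pg/mL has already met the two-visit criterion of below 70 pg/mL for a first reduction. The next lower level is then the second reduction or below: 300/420 = 150/210 = 71% of the full weekly dose.

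**The case against.** The strongest reply is that the practical risk is small and centrally controlled. Sites and sponsor are blinded to iPTH (Sections 3.1 and 5.7), and the IRS issues the dosing adjustments. A child is therefore not restarted at one site and held at another according to which page was read. One rule is presumably programmed and verified by unblinded people. That is a fair narrowing, but the IRS specification and DSMB charter are not among the documents, and a central system still needs one written rule.

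The second reply is that the Synopsis rule is coherent in its own terms. Both texts leave a never-suspended stage 4 child at 35 to 69 pg/mL on drug at a reduced dose. A restart one level down does much the same, further confirmed low values cut the dose again, and the need for a fifth reduction ends dosing. This also stands: the documents do not show the Synopsis rule to be unsafe. The objection to it is that it contradicts Section 5.4 and ignores the stage-specific threshold the plan uses for reduction.

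Third, the upper figures in the illustration are generous. They apply the 60 mcg tail to every active stage 4 subject, although in Cohort 1 only those without a 30% fall at week 12 are titrated up. They also place everyone at the lowest eligible baseline and ignore the three-visit requirement. Treatment for 26 weeks instead of six works the other way.

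Finally, the calcium difference is a single inequality sign, and changing it corrects no demonstrated error. It is worth aligning only because the sentence is being edited anyway.

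**Conclusion.** The inconsistency is real and should be fixed. It affects only suspended stage 4 subjects on active drug, and probably few of them. Fewer than one iPTH suspension is expected at every assumed stage split (0.04 to 0.68), subject to the assumptions of normality, transfer of adult six-week data and lowest eligible baseline. Suspensions for calcium above 11.0 mg/dL cannot be estimated from the documents. Restart is at a reduced dose under either text, and unblinded oversight limits the harm. What remains is a safety threshold in children with two opposite readings. Confidence in the textual conflict is high. Confidence in the frequency is low.

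**What to change.** Use the same sentence in the Synopsis and Section 5.4: after suspension, resume at the next lower dose level when iPTH is at least 35 pg/mL (stage 3 CKD) or at least 70 pg/mL (stage 4 CKD) and corrected serum calcium is below 9.8 mg/dL. Then confirm that the IRS specification and the DSMB charter carry the same rule.

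The cost is one sentence in the Synopsis, one inequality sign in Section 5.4 and a check of two documents, with no added visits or procedures. The downside is that some stage 4 subjects stay off drug longer than under the Synopsis text, as Section 5.4 already requires.

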K/DOQI	Kidney/Disease Outcomes Quality Initiative
MedDRA	Medical Dictionary for Regulatory Activities
MBD	metabolic bone disease
<hr/>	
PD	pharmacodynamic
PE	physical examinations
PK	pharmacokinetic
PP	per-protocol
PT	Preferred Terms
PTH	parathyroid hormone
RCT	randomized clinical trial
SAE	serious adverse event
SAS®	Statistical Analysis Software
SD	standard deviation
SE	standard error
SGOT	Serum glutamic-oxaloacetic transaminase
SGPT	Serum glutamic-pyruvic transaminase
SHPT	secondary hyperparathyroidism
SOC	system organ class
SOP	standard operating procedure
SUSAR	serious unexpected suspected adverse event
$t_{1/2}$	terminal elimination half-life
<hr/>	
TEAE	treatment-emergent adverse events
t_{max}	time to maximum concentration
T_{ss}	time to steady-state concentration
US	United States
Vd/F	volume of distribution

VDI	vitamin D insufficiency
VDRA	vitamin D receptor agonist
VS	vital signs

1 INTRODUCTION

1.1 CTAP101 Capsules

CTAP101 Capsules is an extended-release (ER) oral formulation of calcifediol which was approved as Rayaldee® ER Capsules in June 2016 by the United States (US) Food and Drug Administration (FDA) for the treatment of secondary hyperparathyroidism (SHPT) in adult patients with stage 3 or 4 chronic kidney disease (CKD) and vitamin D insufficiency (VDI), defined as serum total 25-hydroxyvitamin D levels less than 30 ng/mL. EirGen is further developing CTAP101 Capsules for this same indication in pediatric patients.

Calcifediol is 25-hydroxyvitamin D₃, the physiological precursor to the vitamin D hormone, calcitriol (1,25-dihydroxyvitamin D₃). This prohormone is synthesized by the liver from cholecalciferol (vitamin D₃) generated endogenously in skin following exposure to sunlight or obtained from the diet or supplements. Another prohormone, 25-hydroxyvitamin D₂, is synthesized hepatically from ergocalciferol (vitamin D₂), which cannot be produced endogenously, but is obtained from diet or supplements. These two prohormones are collectively referred to as “25-hydroxyvitamin D”. Unless an individual is receiving significant ergocalciferol supplementation, essentially all of the 25-hydroxyvitamin D in blood consists of calcifediol.

1.2 Chronic Kidney Disease

CKD is a worldwide public health problem with steadily increasing incidence, prevalence, and cost [Coresh 2007]. Key factors driving growth of CKD in developed countries include aging populations, the increasing incidence of obesity and its associated complications of hypertension and adult-onset diabetes. CKD is categorized into five successive stages on the basis of estimated glomerular filtration rate (eGFR), with each successive stage representing more advanced disease. Stage 3 CKD is defined by an eGFR in the range of 30 to <60 mL/min/1.73m², and stage 4 CKD is defined by an eGFR in the range of 15 to <30 mL/min/1.73m². CKD afflicts approximately 6-13% of the global population. Despite treatment, CKD continues to be associated with poor outcomes, reflecting the inadequacies of the current standard of care [Nicola 2016, Levey 2005].

1.3 Secondary Hyperparathyroidism

SHPT is a common condition that occurs with advancing CKD and is characterized by excessive production of parathyroid hormone (PTH), hypocalcemia and hypertrophy of the parathyroid glands. SHPT affects 40% to 82% of patients with stage 3 or 4 CKD [Levin 2007]. SHPT requires prompt and effective treatment, as prolonged elevation of PTH causes calcium and phosphorus release from bone, leading to metabolic bone disease and extra-skeletal calcification. In the absence of effective treatment, SHPT becomes progressively more severe and unresponsive to medical treatment as the parathyroid gland becomes hyperplastic and less sensitive to calcium and vitamin D hormone signaling [Nigwekar 2014].

1.4 Pathogenesis of Secondary Hyperparathyroidism

CKD-associated SHPT develops as the result of phosphorus retention, mild hypocalcemia and VDI [Levin 2007]. VDI plays a central role in the pathogenesis of SHPT in CKD [Cunningham 2011]. It limits the normal activation of 25-hydroxyvitamin D to vitamin D hormone (1,25-

dihydroxyvitamin D) in the kidney and in other tissues which contain cytochrome P450 25-hydroxyvitamin D-1 α -hydroxylase (CYP27B1) by reducing the amount of available substrate for conversion. Declining hormone concentrations increase PTH secretion by the parathyroid glands and decrease calcium absorption in the small intestine, leading to hypocalcemia.

1.5 Treatment of Vitamin D Insufficiency

Vitamin D supplementation is recommended by both the K/DOQI and KDIGO Clinical Practice Guidelines, although there is no consensus in regarding how vitamin D supplements should best be administered. Published studies have reported the use of daily doses of vitamin D (either cholecalciferol or ergocalciferol) of 700 to 4,000 International Units (IU), weekly doses of 5,000 to 50,000 IU, and monthly doses of 50,000 to 300,000 IU. Irrespective of the treatment regimen used, no or inadequate reductions in PTH levels have been observed in randomized clinical trials (RCTs) and nutritional vitamin D remains unproven as an effective treatment for SHPT in patients with stage 3-4 CKD [Agarwal 2016, Kalantar-Zadeh 2009]. Immediate-release (IR) formulations of calcifediol, used occasionally in the European Union (EU), have also shown no or inadequate reductions in PTH in clinical trials focused on stage 3-4 CKD.

